**Hypotheses to be tested:**

Changes in activity following pulmonary rehabilitation

1. Compared with baseline, COPD patients participating in outpatient pulmonary rehabilitation will show an increase in directly-measured physical activity

- (minutes per day of walking activity from the DynaPort) at the  $12 \pm 3$  week assessment. (primary hypothesis)
2. Compared with baseline, COPD patients participating in outpatient pulmonary rehabilitation will show increases in upright activity, activity intensity, steps per day, minutes with METs  $> 2$  (from the DynaPort) after  $24 \pm 3$ ,  $36 \pm 3$  and  $48 \pm 3$  weeks
  3. Exploratory: We will analyze the trajectory of physical activity over the 48 weeks after initiating pulmonary rehabilitation.

#### Predictors of baseline physical activity

4. Exploratory: We will analyze predictors of baseline physical activity. Baseline variables tested will include age, gender, body mass index (BMI), six minute walk distance, FEV1, self-efficacy (using the PRAISE questionnaire), motivation for exercise (using the BREQ-2 instrument, questionnaire), MRC dyspnea, health status (using the self-administered Chronic Respiratory Disease (CRQ) questionnaire, anxiety and depression (HADS questionnaire, appendix), sleep efficiency and awakenings (from DynaPort output), functional performance using the Timed Up and Go (TUG) test.

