### **Background and rationale**

Physical activity in COPD patients is reduced, (1) and this inactivity is associated with poor outcome, including increased health care utilization and mortality. (2-5) Bronchodilators, considered a first line therapy of COPD, have documented effectiveness in physiologic function, symptom relief, and exercise capacity enhancement, but apparently do not consistently increase in physical activity. Even pulmonary rehabilitation exercise training, with remarkable effectiveness in increasing exercise capacity, does not consistently increase physical activity.(6, 7) There are probably multiple reasons behind this apparent lack of efficacy, but two important ones are a poor signal-to-noise ratio in accelerometers (used to measure activity) and real problems translating increases in physiologic function (such as increased FEV1 or six minute walk distance) into increases in physical activity. Both of the above are major areas of interest that need to be addressed to improve our care of COPD.

This study will follow physical activity following pulmonary rehabilitation longitudinally over 48 weeks. We will use a state-of-the-art accelerometer, the DynaPort (<https://www.mcroberts.nl/products/movemonitor>), to analyze minutes walking per day

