### **Design:**

This will be predominately a hypothesis-generating study. Its general design is that of a longitudinal study (without a control group) evaluating directly-measured physical activity in COPD patients who had participated in pulmonary rehabilitation. Activity measurements will be at baseline (before exercise training is started), and at approximately 12, 24, 36, and 48 weeks (+/- 3 weeks at each time period) following pulmonary rehabilitation. There will be no direct change, per protocol, in the patient's pharmacological treatment for COPD (controller or rescue inhaler medication) or other medical problems; this treatment will be directed by the patient's health care provider.

Three distinct types of analysis will be performed:

1. Evaluation of changes in physical activity before and after pulmonary rehabilitation

2. Predictors of baseline physical activity
3. Predictors of *change* in physical activity following pulmonary rehabilitation.

This will be an intent-to-treat analysis, providing patients complete 50% or more of the pulmonary rehabilitation sessions. Those dropping out with less than 50% attendance will be dropped from the study.

Dealing with Exacerbations: It is anticipated that patients will have COPD exacerbations over the course of the study. Since exacerbations themselves affect physical activity, activity testing will be postponed for 2 weeks following the clinical end of the exacerbation. We have determined that physical activity returns to close to baseline by two weeks after the exacerbation (Ehsan et al, A Longitudinal Study Evaluating the Effect of Exacerbations on Physical Activity in Patients with Chronic Obstructive Pulmonary Disease. Annals of American Thoracic Society 2013; 10(6):559-64). If two exacerbations occur within the same time block, testing for that period will not be performed, and the last observation will be carried forward. If a patient is hospitalized for an exacerbation, that patient will be dropped from the study.

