### Sample size estimates

Sample size estimates are based on Langer et al. Am J Transpl 2012 and using <http://www.biomath.info/power/ttest.htm>. Patients following lung transplantation were randomized to exercise training or standard care. Walking activity (min/day) from baseline to 12 weeks increased from  $36 \pm 16$  to  $56 \pm 24$  in the treatment group. Assuming a treatment difference, in minutes, of 18 and a SD of 20 and a within-group analysis, an n of ~ 12 would have a power of 0.80 to show this difference. We expect our improvement in walking time with rehabilitation in COPD patients will be less robust. Assuming an increase in activity (minutes per day of walking) of 10 minutes would require an n of 34 to give a power of 0.80, but an improvement of 8 minutes would require 52 patients. Forty evaluable patients appears to be a reasonable number.

Number of subjects: Our goal will be to recruit 40 patients with evaluable data at 12 weeks. Assuming 10 dropouts during rehabilitation, we would need to recruit 50.

Study period: Recruitment over the 6 sites will be over 10 months (~ 40 weeks). Since study follow-up is for 48 weeks per patient, the study will last approximately 84 weeks from first patient in to last patient out.

Activity measurement: We will use the DynaPort MoveMonitor to assess: sedentary activity, upright activity, walking activity, activity intensity, and steps per day. Activity will be measured for 7 consecutive days, 3 days (12 hours per day) minimum. Patients will be asked to wear the devices 24 hours per day, if possible.

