### Protocol synopsis:

1. Patients with COPD entering pulmonary rehabilitation at the study sites will be recruited. Each center will be under its own IRB authority.
2. Rehabilitation will be given per usual pulmonary rehabilitation center protocol; there will be no specific changes in COPD medications, including long acting bronchodilators, short-acting bronchodilators, or inhaled corticosteroids. As is typical with pulmonary rehabilitation, these medications will be managed by the patient's health care provider.

3. Standardized, written post-rehabilitation home exercise recommendations will be given to all patients during rehabilitation and upon completion of the program.
4. Baseline testing:
  - a. Collect information on demographics, baseline testing (see below), list comorbidities
  - b. First measurement of physical activity (before starting pulmonary rehabilitation exercise training), within 6 weeks of beginning pulmonary rehabilitation
  - c. Outcomes testing
5. Weeks from study entry: 12, 24, 36, 48:
  - a. Timing:  $\pm$  3 weeks, except for the 12 week visit, which will be after the end of formal pulmonary rehabilitation, and therefore may occur outside of this 3-week window (rationale: to avoid measuring physical activity during pulmonary rehabilitation days)
  - b. Evaluate for adverse events, list concurrent medications.
  - c. Evaluation for Serious Adverse Events: Evaluation for serious adverse events (SAE) will be made at each study visit if the patient is taking a Boehringer Ingelheim drug. If an SAE is identified on a visit, regardless of causal relationship, it will be reported to Boehringer Ingelheim using the Serious Adverse Event Report (SAE) in Non Interventional Studies (NIS) template within 24 hours or the next business day. The following will be the plan of action for SAE assessment and planning:
    - i. Definitions of adverse events
      - a. An adverse event (AE) is defined as any untoward medical occurrence, including an exacerbation of a pre-existing condition, in a patient in a clinical investigation who received a pharmaceutical

product. The event does not necessarily have to have a causal relationship with this treatment.

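### The baseline-predictor analysis (hypothesis 4) uses only pre-rehabilitation data, yet the attendance and hospitalization drop rules are not switched off for it and it has no analysis set of its own

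*Combined protocol and SAP*

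**What the plan says.** The Design section lists three distinct types of analysis. The second is "Predictors of baseline physical activity". Hypothesis 4 repeats it: "Exploratory: We will analyze predictors of baseline physical activity", followed by a list of baseline variables. The activity outcome is recorded early: the Protocol synopsis specifies "First measurement of physical activity (before starting pulmonary rehabilitation exercise training), within 6 weeks of beginning pulmonary rehabilitation". The table of measurements places every predictor at the week 0, pre-rehabilitation visit; FEV1 may be historical.

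Directly after the list of three analyses, the Design section continues: "This will be an intent-to-treat analysis, providing patients complete 50% or more of the pulmonary rehabilitation sessions". It then adds "Those dropping out with less than 50% attendance will be dropped from the study" and, under the handling of exacerbations, "If a patient is hospitalized for an exacerbation, that patient will be dropped from the study". According to Factors Affecting Study Duration, follow-up lasts about 48 weeks per patient.

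Sample size estimates aims for 40 patients evaluable at 12 weeks: "Assuming 10 dropouts during rehabilitation, we would need to recruit 50". The Data analysis section gives methods for change, trajectory and responder status. It gives neither a method nor an analysis set for hypothesis 4.

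**The concern.** Hypothesis 4 is cross-sectional. Once a patient has a valid baseline recording and the baseline tests, that patient can contribute, whatever happens next. Attendance and freedom from hospitalization have some bearing on an analysis of change after rehabilitation. They have none on an analysis of who is more or less active before it starts. Conditioning hypothesis 4 on them gains nothing and costs records.

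The cost may go beyond precision. Background and rationale says that "this inactivity is associated with poor outcome, including increased health care utilization and mortality", so a rule that removes hospitalized patients may remove less active ones, which is selection on the outcome of the model. Attendance may also depend on motivation, self-efficacy or mood, all of which are among the predictors. That second link is reasoning, not something the plan states.

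**Working it through.** **1. Inputs.** From Sample size estimates: 50 recruited, 10 assumed dropouts during rehabilitation, 40 evaluable at 12 weeks; SD 20 minutes; power 0.80. The plan states no significance level, so two-sided 5% is assumed. It gives no hospitalization rate and no relation between retention and baseline status.

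**2. The plan's own figures.** A paired t-test with SD 20, 80% power and two-sided 5% (exact noncentral t) needs 12, 34 and 52 patients for gains of 18, 10 and 8 minutes. These match the plan. Recruitment also agrees: 40 / (1 − 0.20) = 50. The primary sample size is not in question.

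**3. Records at stake.** If all 10 assumed dropouts are excluded from hypothesis 4, 10/50 = 20% of records go and 40 remain. The 10 covers the rehabilitation period only. If 10% or 20% of the remaining 40 were later hospitalized (assumed rates), 36 or 32 records would remain. If some of the 10 had already reached 50% attendance and were kept, fewer than 10 would be lost.

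**4. Precision.** The standard error ratio is √(50/40) = 1.118, about 12% larger at n = 40. By Fisher's z, the smallest correlation detectable with 80% power is tanh[(1.960 + 0.842)/√(n − 3)], and power for a true r is Φ[atanh(r)·√(n − 3) − 1.960].

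| n | Detectable r | Power, r = 0.40 | Power, r = 0.30 |
|---|---|---|---|
| 50 | 2.802/√47 = 0.409, tanh = 0.39 | 83% | 56% |
| 40 | 2.802/√37 = 0.461, tanh = 0.43 | 73% | 47% |
| 36 (assumed) | 0.45 | 68% | 43% |

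At n = 32 (assumed) the detectable r is 0.48. All these figures are for one correlation at a time.

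**5. Selection.** To see whether a direction of bias can be claimed, take a true r of 0.40 between walking time and one predictor, both normal. Retain the 80% with the highest value of a normal retention score, and let c, from 0.2 to 0.5, be the assumed strength of its correlation with walking, the predictor or both. Two million simulated patients give:

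| Retention related to | r among the retained |
|---|---|
| Both, same sign (c with each) | 0.39 to 0.33 |
| Walking only (predictor only through walking) | 0.397 to 0.382 |
| Walking, uncorrelated with the predictor | 0.403 to 0.423 |
| Both, opposite signs | 0.42 to 0.56 |

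When retention acts only through the predictor, the regression slope of walking on the predictor stays at 0.40 for every c. Bias in the slopes of a correctly specified model therefore requires retention to depend on walking after allowing for the predictors, and the correlation can then move either way.

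**The case against.** The strongest reply is that nothing in the plan says collected baseline data will be discarded. Dropped from the study can mean that follow-up ends, and an intent-to-treat condition has no obvious meaning for a cross-sectional model. This stands in part: a reader might infer that the plan commits to deleting these records, and it does not say so. But the condition directly follows a list that contains hypothesis 4, no exemption appears anywhere, and exclusion is the natural reading. If the text is instead ambiguous, the analysis set could be chosen after the data are seen.

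Second, the 10 of 50 is an assumption about dropout during rehabilitation, made for the primary endpoint. It is not a count produced by the two rules, and a start of 50 presumes that every recruit has a valid baseline recording. This stands, so 20% is an indication.

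Third, a reader might infer that the exclusions pull associations toward zero and cut power well below 73%. The documents do not support that. Depending on how retention relates to walking and the predictor, the correlation barely moves, falls or rises. The steepest falls need retention to correlate 0.5 with both variables, for which the plan offers no evidence.

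Fourth, hypothesis 4 is exploratory in a study described as mainly hypothesis-generating. With 14 predictors (HADS and sleep counted as two each), a full model has 50 − 15 = 35 or 40 − 15 = 25 residual degrees of freedom, so it is thin either way. This limits the weight of the point. It is no reason to give up usable records.

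**Conclusion.** The point holds as a defect in how the analysis set for hypothesis 4 is defined. Followed as written, the Design section conditions a purely pre-rehabilitation analysis on later attendance and hospitalization. If that removes the plan's assumed 10 of 50, the cost is modest: the step from n = 50 to n = 40 shown above. This rests on a two-sided 5% level, single correlations, and all 50 recruits having a valid baseline recording. The true loss may be larger or smaller.

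Selection bias is a possibility, arising if retention depends on baseline activity given the predictors. Neither its size nor its direction follows from the documents. A reader might also infer that hypothesis 4 is explicitly aimed at everyone entering rehabilitation. It names no population: recruitment is of patients entering rehabilitation, while the Design section speaks of those who had participated in it. The case for using all baseline records rests on no later information being needed. The primary analysis is untouched.

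**What to change.** In Design and in Data analysis, state that hypothesis 4 is analysed in all enrolled patients with a valid baseline recording, regardless of later attendance, withdrawal or hospitalization, and that the two drop rules do not define this analysis set. Repeat the analysis in the retained patients as a sensitivity analysis. It would help to name the model, since none is given, and to tabulate baseline activity and predictors for retained and dropped patients so that any selection can be seen.

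This takes two or three sentences and no new data, visits or patients. The small downside is that hypothesis 4 and the change analyses will have different denominators, and both must be reported.

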#### Predictors of *change* in physical activity

5. Exploratory: We will be able to identify responders versus non-responders with respect to: 1) the change in activity at 12 weeks, and 2) the trajectory (over 48 weeks) in these activity measurements; this will include the slopes of change in physical activity. We will then relate baseline variables to responder status. We cannot a priori determine a threshold for physical activity responder status; this will have to be done a posteriori when data are available. We anticipate from the post-lung transplant study the responder threshold will be an increase in 10 minutes walking time per day. Predictor variables are listed above.

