### Data analysis

The primary variable to be assessed will be changes in daily walking activity (in minutes) from baseline to week 12. The statistical approach for this will be a repeated measures analysis of variance using SAS. Covariates may be added, if necessary. We anticipate day of week variation (Sundays have less activity) and seasonal variation (less activity in winter). This will be handled by including these variables as covariates in the analysis. We will also analyze the 24 36 and 48 week endpoints compared to baseline this way. Trajectory changes will be first analyzed by graphs relating activity (in minutes) at each data collection time. We will also analyzed slopes of activity, it possible. Responder non-responder analyses will be performed using logistic analysis with demographics and baseline disease characteristics as potential predictor variables.

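### Predictors of change in walking have one stated method, logistic analysis of responder status with a cut-off set after the data; a baseline-adjusted continuous model should lead instead

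*Combined protocol and SAP*

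**What the plan says.** The Design section lists predictors of change as the third of three analyses and calls the study predominantly hypothesis-generating. The comment that closes that section counts predictors of response as part of the primary intent.

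Hypothesis 5 (Predictors of change in physical activity) is exploratory. It classifies patients as responders on the 12-week change and on the 48-week trajectory, and then: "We will then relate baseline variables to responder status". On the cut-off: "We cannot a priori determine a threshold for physical activity responder status; this will have to be done a posteriori when data are available". From the lung-transplant study it anticipates that "the responder threshold will be an increase in 10 minutes walking time per day". No value is anticipated for the trajectory.

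On predictors: "Predictor variables are listed above". This points to the list under hypothesis 4, which begins "Baseline variables tested will include age, gender, body mass index (BMI), six minute walk distance, FEV1" and does not name baseline walking.

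The Data analysis section gives one method for this aim: "Responder non-responder analyses will be performed using logistic analysis with demographics and baseline disease characteristics as potential predictor variables". On slopes it says "We will also analyzed slopes of activity, it possible", without a model that relates predictors to them. For the change from baseline itself: "The statistical approach for this will be a repeated measures analysis of variance using SAS".

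**The concern.** Grouping a continuous outcome into responders treats a gain of 11 minutes like one of 40, and a gain of 9 like a loss of 20. If change is near normal, this weakens every predictor comparison, and 40 evaluable patients leave little to spare. A hypothesis-generating study depends on ranking its candidates well.

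Two further features add doubt. The cut-off is open until the data are in, so it could in principle be chosen for the associations that it produces. And baseline walking is not among the listed predictors, although change is computed from it. A variable that merely tracks baseline walking, which is what hypothesis 4 looks for, could then appear to predict response.

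**Working it through.** **Inputs from Sample size estimates.** 40 evaluable patients; walking SDs of 16 (baseline) and 24 (week 12), from the lung-transplant study; SD 20 for the within-group analysis; expected gain 10 min/day. Cut-off 10 min/day, from hypothesis 5.

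**The plan's own figures.** A paired t-test at two-sided 5% (alpha is not stated) with SD 20 and power 0.80 gives n = 12, 34 and 52 for gains of 18, 10 and 8 min. This matches the protocol exactly, so the SD of 20 acts as the SD of change.

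**Implied correlation of baseline with week 12.** 20² = 16² + 24² − 2r(16)(24), so r = (256 + 576 − 400)/768 = 0.5625. The correlation of change with baseline is then (0.5625 × 24 − 16)/20 = −0.125, which is weak.

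**Assumed, because the documents give nothing.** Partial correlation of predictor with week-12 walking given baseline, 0.3 to 0.5; predictor-to-baseline correlation c, 0 to 0.5; shape of the distribution.

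**Power, normal change.** Simulation with n = 40, two-sided 5%, r = 0.56, c = 0.3:

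| Partial correlation | 0.3 | 0.4 | 0.5 |
|---|---|---|---|
| Linear, baseline-adjusted | 0.47 | 0.75 | 0.92 |
| Rank test, both residuals | 0.43 | 0.69 | 0.88 |
| Logistic with baseline | 0.35 | 0.56 | 0.77 |
| Logistic, predictor alone | 0.25 | 0.43 | 0.64 |

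Linear minus logistic with baseline is 12, 19 and 15 points here, and 11 to 20 over baseline-to-week-12 correlations of 0.3 to 0.8 and c of 0 to 0.5. Part of the further drop in the last row arises because that model asks a different question. In sample-size terms, for a correlation of 0.4 with change and 80% power, the continuous analysis needs ((1.960 + 0.842)/0.4236)² + 3 ≈ 47 patients. Logistic needs about 70 by simulation.

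**Power, other shapes** (partial correlation 0.4, gain 10; linear / logistic with baseline / rank):
- t with 3 df: 0.80 / 0.84 / 0.90
- Laplace: 0.74 / 0.77 / 0.81
- Lognormal (log-SD about 0.8): 0.77 / 0.79 / 0.94

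With stronger skew (lognormal, log-SD 1) and a mean gain of 18, rank loses to logistic: 0.89 against 0.94 at partial correlation 0.3, and 0.97 against 0.99 at 0.4.

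**Form of the rank test.** If only the outcome is adjusted for baseline, the test's size falls to about 2.5 to 3% at c = 0.5. If the predictor is adjusted too, it is about 5%.

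**Leaving out baseline walking.** Share of trials in which predictor-only logistic flags a predictor that has no effect once baseline is known (normal change):

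| Baseline-to-week-12 correlation | 0.3 | 0.56 | 0.8 |
|---|---|---|---|
| c = 0.3 | 9.1% | 6.4% | 6.9% |
| c = 0.5 | 15.9% | 7.1% | 9.5% |

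With baseline in the model the rate is about 5% (linear) or 6% (logistic). Correlations of 0.3 and 0.8 imply SDs of change of √(832 − 768 × 0.3) = 24.5 and √(832 − 768 × 0.8) = 14.8, not the protocol's 20.

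**Cut-off chosen by its associations.** With 10 min fixed, a null predictor is flagged in 5 to 6% of trials. If one shared cut-off were chosen over 14 null predictors to maximise significant results, two simulations gave 8.5% and 9.4% with three candidate cut-offs, and 10% and 11% with six. If the best cut-off were taken separately for each predictor, the rates would be 10 to 13% and 13 to 18%.

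**Interval width.** Residual SD = 24√(1 − 0.5625²) = 19.84. The 95% half-width per predictor SD is 2.026 × 19.84/√39 = 6.4 min/day at c = 0, and 6.4/√0.75 = 7.4 at c = 0.5.

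**The case against.** The strongest reply is that the item is labelled exploratory, claims no power, and discloses both the late cut-off and a 10-minute expectation taken from outside data. That stands, and it limits the weight of the point.

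The specification is thin rather than closed. The hypothesis 4 list says what it will include, the Background names baseline activity and changes in exercise capacity as factors to explore, and both are measured. A reader might infer that the plan excludes them; it does not. A reader might also infer that omitting baseline walking seriously distorts the results. At the correlation that the protocol's figures imply, it barely does.

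A reader might further infer that the cut-off will be picked to suit the findings. The plan does not say so, and it describes one threshold, so the per-predictor inflation figures do not describe it.

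Nor is the continuous model better in all circumstances: least squares can lose to logistic when change is not normal, and the rank test usually, but not always, beats logistic. More analyses also mean more unadjusted tests. With 14 candidates, by one count of the list, and independent tests at 5%, the chance of at least one false positive is already 1 − 0.95¹⁴ = 0.51.

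What remains is that no stated analysis relates predictors to change on its own scale, for one of three declared aims.

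**Conclusion.** The point holds as a modest recommendation. At n = 40 with roughly normal change, dichotomising at 10 min/day costs about 12 to 20 power points per predictor. This rests on the protocol's lung-transplant SDs carrying over to COPD and on assumed partial correlations of 0.3 to 0.5. Without normality the advantage of least squares can vanish or reverse, and the case then rests on the rank-based check.

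The other two elements are smaller. Leaving out baseline walking raises the false-flag rate to about 7% against 5% at the implied correlation; 9 to 16% needs a correlation of 0.8 or 0.3 together with c = 0.5. Picking one shared cut-off by its associations would give roughly 8 to 11%, but the plan does not propose this. Nothing here touches the primary 12-week comparison or its sample size.

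**What to change.** - **Main exploratory analysis:** regress week-12 walking minutes on baseline walking minutes plus one predictor at a time. Report 95% confidence intervals, labelled as unadjusted for multiplicity.
- **Sensitivity check:** report a Spearman correlation between the baseline-adjusted residuals of the outcome and those of the predictor. Both must be adjusted. State in advance that the linear model leads and that any disagreement will be reported as such.
- **Responder analysis:** fix 10 min/day as the single 12-week cut-off before the data are seen, and keep the logistic analysis as secondary.
- **Trajectory:** use predictor-by-time terms in the planned repeated measures model instead of a slope cut-off.

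The cost is a few lines of analysis text, more analyses to report, and a less simple presentation than a responder rate. No new data, visits or patients are needed. Intervals stay wide, about ±6.5 min/day per predictor SD against an expected mean gain of 10, so the results remain hypothesis-generating.
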